4 INVESTIGATIONAL PLAN

4.1 Overall Study Design and Plan

This is a Phase 2, multicenter, randomized, double-blinded, parallel-group, placebo-controlled study to evaluate the efficacy and safety of upadacitinib in adult subjects with moderate to severe HS.

The duration of the study will be up to 57 weeks and will include an approximately 35-day screening period followed by a 48-week double-blinded treatment period and a 30-day follow up visit after the last dose of study drug.

Subjects who meet eligibility criteria will be randomized in a 2:1 ratio to 1 of the 2 arms as shown below:

- Upadacitinib 30 mg once daily (QD) (N = 40): Daily oral doses of upadacitinib 30 mg from the Baseline visit through Period 1 and Period 2.
- Placebo (N = 20): Placebo for upadacitinib from the Baseline visit up to the Week 12 visit (Period 1). At Week 12, subjects will be switched to blinded upadacitinib 15 mg QD through Period 2.

[figure not shown]

The schematic of the study is shown in Figure 1. Further details regarding study procedures are included in the Operations Manual (Appendix F).

See Section 5 for information regarding eligibility criteria.

The primary efficacy analysis will be conducted when all ongoing subjects have completed their Week 12 visit.

Figure 1. Study Schematic

HiSCR = ≥50% reduction from baseline in the total AN count, with no increase in abscess or draining fistula counts

PBO = placebo; UPA = upadacitinib

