2.1 Individual Treatment Period Visit Activities

This section presents a list of activities performed during each visit, organized by visit. The dot pattern on the upper right indicates the place of the visit in the overall Treatment Period Activity Schedule.

Subjects will be allowed a visit window of \pm 3 days for all study visits (with the exception of the Baseline Visit, as the screening window is a maximum of 35 days) up to the Week 16 visit. Visits after the Week 16 visit will have a visit window of \pm 7 days.

Activities are grouped by category (Interview, Exam, etc.). Further information about each activity is provided in Section 3.

State of Emergency or Pandemic-Related Acceptable Protocol Modifications

During a state of emergency or pandemic situation, if it is not possible for all study procedures to be performed as specified due to travel restrictions or other reasons, the following modifications are allowed:

- If permitted by local regulations, the Institutional Review Board (IRB)/ Independent Ethics Committee (IEC), and the subject, some study visits and/or activities may be performed by phone/virtually. These are indicated by a hashtag (#) in the appropriate visit table(s) below.
- Some study visits and/or activities may be performed by a local clinic/hospital/laboratory. These are indicated by a plus sign (+) in the appropriate visit table(s) below. All procedures performed at local facilities must be performed by appropriately qualified personnel.
- Study visits and/or activities should be performed as scheduled whenever possible. If it is not possible to do so due to the pandemic, the following modifications should be followed:
 - The Screening, Baseline, and Week 12 visits should be performed on-site only.
 - If an activity is missed during a virtual visit, perform the activity at the earliest feasible
 opportunity. Laboratory draws for safety assessments should be obtained as soon as
 feasible and preferably within the protocol-defined visit window for the scheduled visit.
 Blood samples for PK assay that cannot be performed on-site for a specific visit will be
 considered missed.

No use or disclosure outside AbbVie is permitted without prior written authorization from AbbVie.

SCREENING:

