3.7 Patient-Reported Outcomes

Data Collection

Subjects will complete self-administered patient-reported outcome (PRO) instruments. Subjects should be instructed to follow the instructions provided with the instrument(s) and to provide the best possible response to each item. Site personnel shall not provide interpretation or assistance to subjects other than encouragement to complete the tasks. Site personnel will encourage completion of the instrument at all specified time points and will ensure that a response is entered for all items.

PRO instruments that are administered at the site should be completed prior to drug administration and prior to any discussion of AEs or any review of laboratory findings. The subject should complete the questionnaire(s) before site personnel perform any clinical assessments and before any other interaction with site personnel has occurred to avoid biasing the subject's response.

From at least 7 consecutive days prior to the Baseline visit and up to the Week 16 visit, PGA Skin Pain will be collected from subjects using an electronic daily diary and analgesic use using a paper diary. After the Week 16 visit, PGA Skin Pain will be collected for 7 consecutive days leading up to the next scheduled visits as specified in Section 2.1. HSSA will be collected for 7 consecutive days prior to visits specified in Section 2.1. PGA Skin Pain will be collected from subjects electronically every evening using a handheld device provided to the subject at Screening. All data entered on the device will be immediately stored to the device itself, as well as automatically uploaded to a central server. Analgesic use for HS-related pain will be collected from subjects during the same timeframe by completing a paper diary. Data from the pain medication diary will be transcribed into the electronic data capture (EDC) system by study site staff.

Data from the DLQI and HSIA will be collected electronically at the visits specified in Section 2.1. Subjects will use a tablet device at the site to enter the required pieces of information. The electronic tablet device will be programmed to allow data entry for only the visits specified in the protocol and will not allow subjects to complete more than one of the same assessment at any one visit. All data entered on the tablet device will be immediately stored to the devise itself and automatically uploaded to a central server.

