State of Emergency or Pandemic-Related Acceptable Protocol Modifications

During a state emergency or pandemic situation, subject visits may be conducted via phone or video conference. Patient-reported outcomes (DLQI and HSIA) are eligible for completion at these virtual visits, except Baseline and Week 12. If conducted by phone or video conference, sites will read the PRO questions and response options to the subject and record the subject's responses. The subject's ability to view the PRO to understand the questions and response options should be preserved. Sites may send the questionnaires (email or hard copy) to the subjects to allow them to read/understand the questions and responses when the subject is providing responses over the phone. The date and time of PRO data collection should be recorded along with who collected the information.

Patient's Global Assessment of Skin Pain

The PGA Skin Pain (Appendix 7.1) will be used to assess the worst skin pain due to HS. The scoring for PGA Skin Pain is based on an 11-point numerical rating scale (NRS), with ratings for the item ranging from 0 (i.e., no skin pain) to 10 (i.e., skin pain as bad as you can imagine). Patients are asked to respond to the items based on a recall period of "the last 24 hours." The weekly average score is calculated based on the 7 available daily scores from the days within each visit window that were closest to the nominal day.

Hidradenitis Suppurativa Symptom Assessment Questionnaire

The HSSA (24-hour recall) is a 9-item PRO questionnaire (Appendix 7.2) developed to assess the primary symptoms of HS in the 7 consecutive days prior to assessments. Each item of the HSSA is scored on an 11-point (0 to 10) NRS, where 0 represents no symptoms and 10 represents extreme symptom experience. In this way, item scores can be generated to characterize the subject's experience at a symptom level. Additionally, Items 1-9 can be scored together to create a Total Symptom Score to characterize an overall symptom experience by averaging the scores collected from the non-missing items collected at the same assessment. The weekly average score is calculated based on the 7 available daily scores from the days within each visit window that were closest to the nominal day.

Hidradenitis Suppurativa Impact Assessment Questionnaire

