9.0 Efficacy Analyses

9.1 General Considerations

All efficacy analyses will be conducted in ITT Population in each period. All tests will be 1-sided at an alpha level of 0.05.

The Primary Analysis will be conducted after all ongoing subjects have completed Week 12, data pertaining to Period 1 has been cleaned, and a database lock has occurred for the purpose of efficacy and safety analysis in Period 1. This is the only and final efficacy analysis for Period 1.

In Period 1, all categorical variables at Week 12 and experience of flare in Period 1 will be analyzed using one sample Chi-square test comparing with historical placebo rate. Supplemental analyses will be conducted to compare in-trial data in upadacitinib group vs in-trial placebo data combined with historical placebo data for primary and secondary endpoints, and compare in-trial data in upadacitinib group vs in-trial placebo data for all categorical endpoints.

Continuous variables will be analyzed using Mixed-Effect Model Repeat Measurement (MMRM) (for endpoints other than DLQI) and Analysis of Covariance (ANCOVA) (for

DLQI) comparing with historical placebo mean change from Baseline at Week 12. Supplemental analyses will be conducted to compare in-trial data in upadacitinib group vs in-trial placebo data.

Long-term efficacy in the Period 2 will be summarized using the observed case approach.

Any subject who is randomized based on a wrong stratum will be analyzed according to the actual stratum the subject belongs to.

For variables other than PGA Skin Pain NRS, "Baseline" refers to the last non-missing observation on or before the date of the first administration of study drug or the date of randomization if no study drug is given. The "Baseline" of PGA Skin Pain NRS is defined as the last non-missing weekly average score, calculated based on the daily scores from the past 7 days (with non-missing values in 4 or more days of the 7 day period), before the date of the first administration of study drug or on or before the date of randomization if no study drug is given.

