9.4 Secondary Efficacy Analyses

9.4.1 Main Analyses of Secondary Efficacy Endpoints

The secondary endpoint NRS30, defined as the achievement of at least 30% reduction and at least 1 unit reduction from Baseline in Patient's Global Assessment (PGA) of Skin Pain (numeric rating scale [NRS]) – at worst at Week 12 among subjects with baseline NRS ≥ 3 .

NRS30 will be analyzed using the same method as for the primary endpoint and comparing with the historical placebo rate (22.5%) at Week 12. The historical placebo rate of 22.5% is assumed based on the response rate of placebo subjects from the two Humira studies (Study M11-313 and Study M11-810), who satisfied the same eligibility criteria.

The same supplemental analysis to compare upadacitinib 30 mg group vs in-trial placebo group combined with pre-selected placebo subjects' data from the three existing trials will also be performed as described in Section 9.3.3. The actual number of synthetic placebo subjects is determined as below (simulation details can be found in [Appendix F](#) and the list of matching subjects can be found in [Appendix G](#)):

In-Trial Placebo Rate	Number of Synthetic Placebo Subjects
$\leq 36\%$	68
$>36\%$ and $\leq 37\%$	23*
>37	0

* The 23 subjects with the highest rank in [Appendix G](#) Table B will be used in the analysis.

Comparison between the in-trial data of the upadacitinib group and the in-trial placebo subjects will also be performed. The analysis method will be the same as described in Section 9.3.3.

In addition, analgesic use will be handled as follows:

- Prohibited analgesic (including opioids): A subject will be counted as a non-responder from the day that the subject initiates prohibited analgesic to 5 days after the end of such analgesic use.
- Protocol-allowed analgesic use:
 - A subject who enter the study without concomitant analgesic will be counted as a non-responder from the day that the subject initiates a protocol-allowed analgesic to 2 days after the end of such analgesic use.
 - A subject who entered the study on a stable dose of a protocol-allowed concomitant analgesic will be counted as a non-responder from the first day of an analgesic dose increase to 2 days after the end of the dose increase.

The NRI-C will be the primary approach for missing data handling in the analysis of the secondary efficacy endpoint. NRI-NC will be used as sensitivity analysis.

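### As written, the Week 12 pain average of placebo subjects includes days after their switch to upadacitinib 15 mg, which affects the supplemental NRS30 comparisons but not the main test

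*Protocol*

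**What the plan says.** Operations Manual Section 3.7 (Protocol Appendix F) gives the only post-baseline scoring rule for PGA Skin Pain: the weekly score is the mean of the "7 available daily scores from the days within each visit window that were closest to the nominal day". The same section sets the collection: "From at least 7 consecutive days prior to the Baseline visit and up to the Week 16 visit, PGA Skin Pain will be collected", and "PGA Skin Pain will be collected from subjects electronically every evening using a handheld device". The Activity Schedule (Protocol Appendix D) puts Week 12 at Day 85. Operations Manual Section 2.1 allows plus or minus "3 days for all study visits" up to Week 16, apart from Baseline.

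For the placebo arm, Protocol Section 4.1 states: "At Week 12, subjects will be switched to blinded upadacitinib 15 mg QD through Period 2".

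SAP Section 9.1 defines the Baseline pain score by looking backward: "calculated based on the daily scores from the past 7 days (with non-missing values in 4 or more days of the 7 day period"). It has no counterpart for post-baseline visits. SAP Section 9.4.1 tests NRS30 in the 30 mg arm against a fixed historical rate of 22.5%. It adds two supplemental comparisons, one with the in-trial placebo arm and one with that arm plus borrowed historical subjects. The observed in-trial placebo rate sets the number borrowed: 68 up to 36%, 23 above 36% and up to 37%, and 0 above 37%.

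**The concern.** The rule is symmetric about the nominal day, and diary scores exist on both sides of it. For placebo subjects the nominal day is also when active treatment begins. A score meant to describe 12 weeks of placebo would then be partly measured on upadacitinib 15 mg, by an amount that depends on when the visit took place.

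NRS30 is the only secondary endpoint. The randomised comparison is the one analysis of it that needs no historical assumption, and here its control arm would be partly treated. The same placebo rate also selects the borrowing tier, so the fault could change which subjects enter the combined analysis.

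**Working it through.** **Plan's own figure.** The documents give no figure for the averaging window, so there is none to reproduce. The SAP's power figures for the comparisons at stake are checked in step 3.

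**Step 1: which days are averaged.** Inputs: nominal Day 85 (Appendix D); visit window of 3 days either side (Operations Manual 2.1); evening scores through Week 16 (Operations Manual 3.7). 85 − 3 = 82 and 85 + 3 = 88, so Days 82 to 88, exactly 7 days. A wider window that contains these days gives the same set if the diary is complete, because they are the 7 nearest to Day 85.

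For a switch on Day v, 88 − v scores fall on later days. The count is 89 − v if the evening score on the switch day follows the first 15 mg dose.

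| Switch day | Later days only | With switch-day evening |
|---|---|---|
| 82 | 6 of 7 | 7 of 7 |
| 83 | 5 | 6 |
| 84 | 4 | 5 |
| 85 | 3 | 4 |
| 86 | 2 | 3 |
| 87 | 1 | 2 |
| 88 | 0 | 1 |

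With a backward window (Days 78 to 84 for a Day 85 visit) the count is 0 of 7.

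**Step 2: the borrowing rule.** SAP Appendix F assumes 23 placebo subjects. 8/23 = 34.8% gives 68 borrowed subjects and 9/23 = 39.1% gives 0, so one responder moves the analysis across both cut-offs. 23 is an upper limit, since NRS30 requires a baseline NRS of at least 3. With 22 subjects, for example, 8/22 = 36.4% gives 23 and 9/22 = 40.9% gives 0.

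**Step 3: power if the placebo rate rises.** SAP Appendix F, Section 3.2, takes 46% on upadacitinib with groups of 45 and 23. Simple pooled formula, one-sided alpha 0.05: power = Φ{[p1 − p2 − 1.645·√(p̄(1 − p̄)(1/45 + 1/23))] / √(p1q1/45 + p2q2/23)}.

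| Placebo rate | Simple formula, in-trial only | SAP simulation, in-trial only |
|---|---|---|
| 26% | 0.48 | 0.603 |
| 31% | 0.32 | 0.434 |
| 36% | 0.19 | 0.279 |

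The levels differ. The SAP simulates a stratified test whose false positive rate is 0.077 at 26%, above the nominal 0.05. Both columns fall steeply. At 36% the SAP gives 0.542 with 68 matched subjects, against 0.279 with none.

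**Step 4: illustration of size, on assumed values.** Assume a placebo NRS30 rate of 26% without post-switch days, baseline pain of mean 5.5 and SD 1.6 limited to 3–10, SD of percent change 30 to 40 points, and every visit on Day 85. Assume an extra fall of 5 to 20 percentage points on post-switch days. The averaged reduction is the pre-switch reduction plus (k/7) × extra fall, with k = 3 or 4.

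| Extra fall | Placebo rate | Chance of at least 9/23 |
|---|---|---|
| none | 26% | 12% |
| 5 points | 27.7–29.2% | 16–21% |
| 10 points | 29.6–32.6% | 22–32% |
| 20 points | 33.4–39.7% | 35–60% |

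The documents supply neither the extra fall nor the SD, so this shows sensitivity and does not estimate the bias.

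**Step 5: the main test.** The 30 mg arm takes the same dose before and after Day 85 and the comparator is a constant, so no placebo score enters.

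**The case against.** The strongest reply is that the analysis window may stop at the switch. SAP Appendix E refers to pre-specified visit windows and, in its Section 2.4, to an SPP-specified window within the particular study period. Placebo treatment in Period 1 ends at the Week 12 visit, and the Period 1 lock covers Period 1 data. A scheduling window of exactly 7 days would also leave the closest-day rule nothing to choose between, which suggests that a different window was meant. The identical sentence scores the HSSA, which is collected only in the 7 days before visits. If the window ends with Period 1, the closest scores are the trailing ones and no post-switch day enters.

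This is possible, and a reader should not infer that the sponsor's analysis certainly uses post-switch days. But no such cut-off appears in the protocol or SAP, and the written rule yields the opposite. Where the SAP wanted a cut at the first Period 2 dose it wrote one, for Period 1 adverse events (Section 10.2.1).

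It is also fair to object that counting days measures exposure and not effect, and that the 8/23 to 9/23 step shows mainly how coarse the borrowing rule is. Both points stand.

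**Conclusion.** Taken as written, with complete diaries, the plan puts active-treatment days into the Week 12 pain score of placebo subjects: 3 or 4 of 7 for an on-time visit, ranging from 0 to 7 over the allowed visit days. This should be corrected, and it goes beyond missing detail because the stated rule gives the wrong days. The affected results are the supplemental in-trial and combined-placebo NRS30 comparisons and the choice of 68, 23 or 0 borrowed controls.

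Three stronger readings are not supported.

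- A reader might infer that the secondary endpoint as a whole is compromised. The main test against 22.5% is untouched.
- A reader might infer a bias in favour of upadacitinib. If 15 mg relieves pain, the placebo rate rises and the difference shrinks, so the likely direction is against the drug. The size cannot be stated.
- A reader might infer that the analgesic rule in SAP Section 9.4.1 needs the same repair, by dropping flagged days from the average. That would loosen it. A subject who starts a prohibited analgesic on Day 83 is a non-responder on Day 85 under the SAP. If flagged days were dropped from Days 78 to 84, 5 usable days (78 to 82) would remain and the subject could count as a responder.

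**What to change.** In the SAP, define the Week 12 PGA Skin Pain score for both arms as the mean of the 7 days ending the day before the first Period 2 dose. For subjects with no Period 2 dose, such as those who stop study drug but stay in follow-up, end the window the day before the Week 12 visit, or on Day 84 if there is no visit. Apply the Baseline completeness rule, "with non-missing values in 4 or more days of the 7 day period". Reconcile the sentence in Operations Manual Section 3.7 with this definition, including its use for the HSSA, whose collection is already limited to the days before visits. Leave the analgesic non-responder rule as it stands.

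The cost is one definition and its programming before the Period 1 database lock. The daily scores are already collected. For an on-time visit with same-day dosing, the centre of the window moves from Day 85 to Day 81 in both arms; the 30 mg arm is on the same treatment throughout.

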The HSIA is an 18-item PRO questionnaire (Section 7.3) developed to assess the impact of HS on the daily lives of subjects in the 7 days prior to the assessment. Items 1-16 of the HSIA are scored on a 0 to 10 NRS, where 0 represents no impact and 10 represents extreme impact. In this way, item scores can be generated to characterize the subject's experience at an individual impact level. Additionally, Items 1-16 characterize the overall impact of HS and can be scored together to create a weekly Overall HSIA score. The Overall HSIA score is generated by summing the completed individual impact, item-level scores collected on the same day, and dividing that sum by the total number of completed responses (i.e., the Overall HSIA score is an average). The Overall HSIA score will only be derived if eight or more (i.e., at least 50%) of responses are available (and adjusting the denominator to match the number of completed items). Items 17 and 18 utilize an open field where patients are asked to fill in a number, and are not included in the Overall HSIA score. Instead, a separate mean score for the hours worked (Item 17) or hours missed at school or work (Item 18) will be calculated. If the response is "Not Applicable" for any of the Items 13-14 or 16-18 then the subject will be deemed as "not applicable" for calculating scores.

Dermatology Life Quality Index

The DLQI is a 10-item validated questionnaire (Section 7.4) used to assess the impact of HS disease symptoms and treatment on quality of life (QoL). It consists of 10 questions evaluating impact of skin diseases on different aspects of a subject's QoL over the prior week, including symptoms and feelings, daily activities, leisure, work or school, personal relationships, and the side effects of treatment. Each item is scored on a 4-point scale (0 = not at all/not relevant; 1 = a little; 2 = a lot; and 3 = very much). Item scores are added to provide a total score, ranging from 0 to 30, with higher scores indicating greater impairment of QoL. For general inflammatory skin conditions, a change in DLQI score of at least 4 points is considered the minimum clinically important difference (MCID).

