13. Over the **past 7 days**, how much did your feelings about your HS limit your desire to have sex (for example, because you felt unattractive, embarrassed, self-conscious, etc.)?

[figure not shown]

If this question is not applicable for you, please press "next."

[figure not shown]

14. Over the **past 7 days**, how much was your ability to have sex limited because of your HS symptoms (for example, pain, cysts, drainage, flare ups, bleeding, etc.)?

If this question is not applicable for you, please press "next."

[figure not shown]

15. Over the past 7 days, how satisfied have you been with your HS medications?

16. Over the **past 7 days**, how bothered did you feel by the scars from your past HS surgery/surgeries?

If this question is not applicable for you as you have not had surgery for your HS, please press "next."

17. Over the past 7 days, how many hours did you spend at work or school?

	please press "next."
	Hours
18.	Over the past 7 days , how many hours did you miss from work or school because of your HS? Include hours you missed on sick days, times you went in late, left early, etc., because of your HS.
	If this question is not applicable for you as you are not employed nor do you attend school, please press "next."
	Hours

Source: AO-AV141778-HSIA-English-USA-Version 2-for electronic use; 03 Feb 2020

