9.5 Additional Efficacy Analyses

9.5.1 Additional Categorical Endpoints in Period 1

The analysis of flare during Period 1 will be performed using the same method as for the primary endpoint, comparing with historical placebo rate of the occurrence of flare in 12 weeks (34%). The historical placebo rate is assumed based on the response rate of placebo subjects from the two Humira studies (Study M11-313 and Study M11-810), who satisfied the same eligibility criteria. A supplemental analysis will be performed to compare upadacitinib 30 mg and in-trial placebo group.

9.5.2 Additional Continuous Endpoints in Period 1

Continuous endpoints except for DLQI will be analyzed using MMRM including observed measurements at all visits, as described in Section 9.2. For HSSA total score, HS-related swelling, odor, worst drainage, and HSIA at Week 12, the comparison will be made between upadacitinib 30 mg group and the historical change from baseline at Week

12 values of -0.72, -0.8, -0.72, -0.89 or -0.83 (HSIA historical value is the average of Week 8 and Week 16 since there is no Week 12 measurement), respectively, using MMRM. The historical change from baseline at Week 12 values are obtained based on the placebo subjects from Risankizumab Study M16-833, who satisfied the same eligibility criteria.

For change from baseline in DLQI at Week 12, the comparison will be made between upadacitinib 30 mg group and historical change from baseline (-2.5) using an ANCOVA model. The historical change from baseline of -2.5 is assumed based on the mean change from Baseline of placebo subjects from the two Humira studies (Study M11-313 and Study M11-810), who satisfied the same eligibility criteria.

Continuous endpoints will also be analyzed using MMRM for endpoints other than DLQI and ANCOVA for DLQI to compare upadacitinib 30 mg QD with in-trial placebo group.

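### The HSIA scoring text contradicts itself on not-applicable answers: one rule scores the subject, the other, read literally, does not

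*Protocol*

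**What the plan says.** The Operations Manual (protocol Appendix F), Section 3.7, gives the only HSIA scoring rules in the two documents. In order:

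- Items in the score: "Items 1-16 characterize the overall impact of HS and can be scored together to create a weekly Overall HSIA score".
- Direction: "Items 1-16 of the HSIA are scored on a 0 to 10 NRS, where 0 represents no impact and 10 represents extreme impact".
- Minimum data: "The Overall HSIA score will only be derived if eight or more (i.e., at least 50%) of responses are available", with a provision for "adjusting the denominator to match the number of completed items".
- Items 17 and 18 (hours at, and hours missed from, work or school) are outside the Overall score and each gets its own mean.
- Last sentence, on a not-applicable response: "for any of the Items 13-14 or 16-18 then the subject will be deemed as 'not applicable' for calculating scores". It does not say which scores it governs.

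In the questionnaire (Section 7.3), items 13 and 14 on sex may be not applicable. Item 16, on surgical scars, carries the instruction "If this question is not applicable for you as you have not had surgery for your HS", and item 18 has a similar one for people neither employed nor in school. In each case the subject presses next.

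The SAP has no HSIA scoring rule. Sections 9.2.2 and 9.5.2 analyse change from Baseline in HSIA by MMRM, against a fixed historical placebo change of -0.83 from Study M16-833 and against in-trial placebo.

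**The concern.** Two rules in one paragraph give opposite results for the same subject. The completed-items rule tolerates up to eight unanswered items. The last sentence, as worded, acts on the subject rather than the item, covers plural scores, and is triggered by any one of five items. Two of those five do not enter the Overall score at all. A programmer could implement either version and claim to follow the text.

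At stake is who is in the HSIA analysis. The conditions that trigger the last sentence are ordinary ones: no previous HS surgery, no job or studies, or a sex item that does not apply. If such subjects are unscored, the endpoint describes a selected subset. That subset may also change between visits as work or personal circumstances change. The comparison with -0.83 is then sound only if Study M16-833 handled not-applicable responses in the same way, and the documents do not say whether it did.

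**Working it through.** **1. The stated threshold.** The text equates eight responses with 50%. 8/16 = 50.0%, whereas 8/18 = 44.4%. The threshold is therefore set on items 1 to 16, consistent with items 17 and 18 being outside the Overall score.

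**2. The two rules applied to one subject.** Take a subject who answers everything that applies. Only items 13, 14 and 16 are both inside the Overall score and named in the last sentence, so at most three of the 16 can be lost this way.

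| Not applicable | Responses among items 1-16 | Completed-items rule (at least 8) | Last sentence, read literally |
|---|---|---|---|
| none | 16 | scored | scored |
| one of 13, 14, 16 | 16 - 1 = 15 | scored | not scored |
| two of them | 16 - 2 = 14 | scored | not scored |
| all three | 16 - 3 = 13 | scored | not scored |
| 17 or 18 only | 16 | scored | not scored |

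The rules disagree in every row but the first. Not-applicable responses alone can never breach the eight-response minimum. A subject with all three would need six further blanks to fall below it (13 - 6 = 7).

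**3. What an unscored form does in the model.** In SAP 9.2.2 the outcome is change from Baseline and the Baseline value is a covariate. A subject with no Baseline score therefore contributes nothing at any visit. In Period 1 the HSIA is collected at Baseline, Week 4 and Week 12 (protocol Appendix D). Elective surgery is not allowed until after the Week 16 visit (protocol Section 6.2), so a subject never operated on at Baseline will usually still be so at Week 12. Under the literal reading that subject is out of the HSIA analysis altogether.

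**4. Size.** The documents give no rate of not-applicable responses. Purely as an assumed range, suppose a proportion p of subjects has at least one at Baseline. The literal rule leaves n x (1 - p) scored:

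- p = 10%: 40 x 0.9 = 36 on upadacitinib and 20 x 0.9 = 18 on placebo.
- p = 70%: 40 x 0.3 = 12 on upadacitinib and 20 x 0.3 = 6 on placebo.

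Item-level handling leaves 40 and 20 at any p, if the forms are otherwise complete. The range shows only that the choice of rule could matter. It is not an estimate.

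**The case against.** The strongest reply is that the last sentence was never meant to void the Overall score. It follows directly after the separate means for items 17 and 18, and the paragraph also speaks of item-level scores. It can therefore be read as removing a subject only from the score of the item that does not apply. Pressing next leaves the item uncompleted, which is just what an adjusted denominator handles. Sites are told to see that every item is answered, so skips for not applicable would be a main source of incomplete forms, and the literal reading would leave the eight-response rule little to do. It would also let items 17 and 18 cancel a score they do not enter.

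Much of this stands. A reader might infer that the plan definitely excludes never-operated or non-working subjects. The documents do not support that, and the inference is weakest for items 17 and 18. What the reply does not do is remove the conflict. The sentence refers to the subject and to scores in the plural, and it groups three items inside the Overall score with two outside it. The item-level reading is plausible but unstated.

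A reader might also infer that item 15 is scored in the wrong direction. It asks "how satisfied have you been with your HS medications", it is averaged with the others, and no reversal is mentioned. That cannot be called an error: its response anchors are in a figure not shown, and Section 3.7 states the same 0-to-10 impact direction for all of items 1 to 16. If the anchors did run the other way, an assumed 3-point gain in satisfaction would move a 16-item mean by 3/16 = 0.19 upwards instead of downwards, a swing of 0.38. If they already run from best to worst, the effect is zero.

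Nor is a mismatch with the historical value shown. SAP 9.5.2 explains that the "HSIA historical value is the average of Week 8 and Week 16 since there is no Week 12 measurement" and that the placebo subjects met the same eligibility criteria. It is silent on how not-applicable responses were scored there. The comparison with in-trial placebo uses one scoring rule for both arms, whichever rule that is.

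**Conclusion.** The contradiction is real and can be read off a single paragraph. For every otherwise complete subject with a not-applicable response to item 13, 14 or 16, at least 13 of 16 responses exist, yet the two rules disagree on whether an Overall HSIA score exists. The SAP leaves it open. Exclusion is one reading and not a certainty.

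The loss cannot be sized from the documents. Multiplying assumed rates for surgery, work and the two sex items would give a figure, but those rates have no source here, and items 13 and 14 would tend to be not applicable together rather than independently.

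This is a minor point. It touches one additional endpoint, change from Baseline in HSIA. The primary analysis (HiSCR), the secondary analysis (NRS30) and the sample size do not depend on it. The direction of item 15 is only something to confirm.

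**What to change.** Replace the last scoring sentence in Operations Manual 3.7 with the following, and repeat it in SAP 9.5.2 so that the programmed rule is prespecified:

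> A not-applicable response to items 13, 14 or 16 is treated as not completed for that item only; the Overall HSIA is still derived if at least 8 of items 1-16 are completed. A not-applicable response to item 17 or 18 affects only that item's mean.

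Then confirm that the -0.83 from Study M16-833 was scored by the same rule, and re-derive it if not. Check that the item 15 response scale runs from 0 for no impact to 10 for extreme impact, and state its direction in the scoring text.

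The cost is two sentences, one look at the item 15 anchors and, at most, a re-run of one reference mean from existing data. No new data are needed. It should be settled before the Period 1 database lock.
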